9. RESEARCH METHODS

9.1. Study design

Retrospective, multicenter, non-interventional, observational and descriptive study.

It will by no means interfere with the investigator's decision on the most appropriate medical care or treatment for the patient or carrier.

The variables collected are consistent with the objectives of the study and will be described in more detail in Section 9.3:

Primary objective	Primary variables
To determine the efficacy of tafamidis free acid 61 mg in ATTRv patients with neurologic involvement included in studies B3461028 and/or LTE (B3461045) in Spain through changes in the NIS scale at 12 months.	Neuropathy Impairment Score (NIS)
Secondary objectives	Secondary variables
To determine the efficacy of tafamidis 61 mg in ATTRv patients with neurologic involvement included in studies B3461028 and/or LTE (B3461045) in Spain using additional non-cardiac variables at 6, 12, 18, 24 and 36 months after the start of treatment.	
 - NIS at 6, 18, 24 and 36 months - NIS-LL, Norfolk QoL-DN, COMPASS-31 and FAP-RODs, FAP - % of patients who do not have stage progression in the PND score

PFIZER CONFIDENTIAL

	
 - % of patients responding to treatment (defined as <4p in NIS and <2p in NIS-LL) - R-R Range Variability - mBMI - Amplitude of the potentials measured in sural sensory and ulnar, tibial and peroneal motor NCS

To determine the efficacy of tafamidis free acid 61 mg in ATTRwt patients with neurological symptoms included in studies B3461028 and/or LTE (B3461045) in Spain, through non-cardiac variables at 6, 12, 18, 24 and 36 months after treatment initiation.
	
 - NIS, NIS-LL, Norfolk QoL-DN, COMPASS-31 and FAP-RODs, FAP - % of patients who do not have stage progression in the PND score - % of patients responding to treatment (defined as <4p in NIS and <2p in NIS-LL) - R-R Range Variability - mBMI. - Amplitude of the potentials measured in sural sensory and ulnar, tibial and peroneal motor NCS

To describe the extra-cardiac characteristics of ATTRv and ATTRwt patients included in studies B3461028 and/or LTE (B3461045) in Spain with mixed phenotype treated with tafamidis free acid 61 mg.
	
 - Demographic variables - Age of onset symptoms and at diagnosis - Neurological and extra-cardiac clinical variables

This study, despite the limited sample size, will provide data on the efficacy of tafamidis free acid 61 mg in hereditary ATTR and wt patients with neurologic involvement.

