8. RESEARCH QUESTION AND OBJECTIVES

Based on the outcomes from previous studies (Coelho T, et al; Maurer MS, et al)^{15,17}, the hypothesis of the present study is that tafamidis free acid 61 mg decreases the progression of polyneuropathy caused by transthyretin amyloidosis in ATTRv and ATTRwt patients with neurological or mixed phenotype.

The study's primary objective is:

- To determine the efficacy of tafamidis free acid 61 mg in ATTRv patients with neurologic involvement included in studies B3461028 and/or LTE (B3461045) in Spain through changes in the NIS scale at 12 months.

The **secondary objectives** of this study are:

- To determine the efficacy of tafamidis 61 mg in ATTRv patients with neurologic involvement included in studies B3461028 and/or LTE (B3461045) in Spain using additional non-cardiac variables at 6, 12, 18, 24 and 36 months after the start of treatment.
- To determine the efficacy of tafamidis free acid 61 mg in ATTRwt patients with neurological symptoms included in studies B3461028 and/or LTE (B3461045) in Spain, through non-cardiac variables at 6, 12, 18, 24 and 36 months after treatment initiation.
- To describe the extra-cardiac characteristics of ATTRv and ATTRwt patients included in studies B3461028 and/or LTE (B3461045) in Spain with mixed phenotype treated with tafamidis free acid 61 mg.

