9.7. Data analysis

Detailed methodology for summary and statistical analyses of data collected in this study will be documented in a Statistical Analysis Plan (SAP), which will be dated, filed and maintained by the sponsor. The SAP may modify the plans outlined in the protocol; any major modifications of primary endpoint definitions or their analyses would be reflected in a protocol amendment.

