12 ANALYSIS OF THE OBJECTIVES

12.1 Primary objective

“To determine the efficacy of Tafamidis free acid 61 mg in ATTRv patients with neurologic involvement included in studies B3461045 and/or LTE (B3461045) in Spain through changes in the 12-month NIS scale”

Primary variable: Neuropathy Impairment Score (NIS).

NOTE: ATTRv patients are considered to be those who have indicated “Mutation” in the genotype (Data related to the disease at diagnosis).

See resolution of this objective in 10.3.1 (month 12).

Additionally, the results will be presented for the percentage of patients responding to treatment of the change at month 12 with respect to the initial value. The N and % of patients responding to treatment will be calculated, defining responder as:

- change at 12 months compared to the initial data <4p in NIS, patients who have obtained less than 4 points in the NIS in month 12

Patients who do not meet the previous condition will be considered non-responders. If complete data is not available, the value will be left as missing.

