 - change at 24 months from baseline <4p in NIS-LL, patients who have achieved less than 4 points in the NIS-LL at Month 24.
 - change at 36 months from baseline (<12p in NIS and <6p in NIS-LL), patients who

have achieved less than 12 points in the NIS and simultaneously less than 6 points in the NIS-LL at Month 36.

Patients who do not meet the previous condition in each month will be considered non-responders. If complete data is not available, the value will be left as missing.

– **NIS and NIS-LL:** Results will be presented in each month, defining responder as:

- change at 6 months from baseline (<2p in NIS and <1p in NIS-LL), patients who have achieved less than 2 points in the NIS and simultaneously less than 1 point in the NIS-LL at Month 6.
- change at 12 months from baseline (<4p in NIS and <2p in NIS-LL), patients who have achieved less than 4 points in the NIS and simultaneously less than 2 points in the NIS-LL at Month 12.
- change at 18 months from baseline (<6p in NIS and <3p in NIS-LL), patients who have achieved less than 6 points in the NIS and simultaneously less than 3 points in the NIS-LL at Month 18.
- change at 24 months from baseline (<8p in NIS and <4p in NIS-LL), patients who have achieved less than 8 points in the NIS and simultaneously less than 4 points in the NIS-LL at Month 24.
- change at 36 months from baseline (<12p in NIS and <6p in NIS-LL), patients who have achieved less than 12 points in the NIS and simultaneously less than 6 points in the NIS-LL at Month 36.

In this case, patients who do not meet the previous two conditions in each month will be considered non-responders. If complete data is not available (NIS and NIS-LL), the value will be left as missing.

- R-R Range Variability (section 10.4)
- mBMI (section 10.2).
- Amplitude of the potentials measured in sural sensory and ulnar, tibial and peroneal motor NCS (section 10.4)

To the extent possible, parametric (paired t-test) or non-parametric (Wilcoxon) statistical tests will be performed, depending on the sample distribution, to study whether there are differences in the unit change rate for pre- and post-treatment previous numeric variables (total and subgroups).

12.2.2 Secondary objective 2

“To determine the efficacy of Tafamidis free acid 61 mg in ATTRwt patients with neurological symptoms included in studies B3461045 and/or LTE (B3461045) in Spain, through non-cardiac variables at 6, 12, 18, 24 and 36 months after treatment initiation.”

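### The SAP scales the protocol's undated responder limits with time without a rationale, and carry-forward then lets a Month 12 failure become a later responder on no new data

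*Protocol*

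**What the plan says.** **Protocol.** The primary objective (section 8) is assessed "through changes in the NIS scale at 12 months" and has no responder rule. Responder status is a secondary variable in section 9.1, for ATTRv and for ATTRwt: the percentage "of patients responding to treatment (defined as <4p in NIS and <2p in NIS-LL"). The ATTRv objective it serves is studied "using additional non-cardiac variables at 6, 12, 18, 24 and 36 months after the start of treatment", and the ATTRwt objective has the same months. The rule names no month and does not say whether the points are a change or a score. Section 9.7 lets the SAP modify the plan, but "any major modifications of primary endpoint definitions or their analyses would be reflected in a protocol amendment".

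**SAP.** Section 12.1 keeps the NIS change analysis and then says "Additionally, the results will be presented for the percentage of patients responding to treatment", using NIS alone: "change at 12 months compared to the initial data <4p in NIS, patients who have obtained less than 4 points in the NIS". Section 12.2.1 (ATTRv) gives NIS, NIS-LL and composite rules for each month. Section 12.2.2 (ATTRwt) gives the composite only. The composite limits (NIS/NIS-LL) are 2/1, 4/2, 6/3, 8/4 and 12/6 at Months 6, 12, 18, 24 and 36, the last worded "change at 36 months from baseline (<12p in NIS and <6p in NIS-LL"). That Month 36 wording also stands under the NIS-LL heading, where Months 6 to 24 use NIS-LL alone.

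Section 6.1.1 fills the visit months. Values up to the follow-up date are interpolated in a straight line from the start of treatment. If there is only one follow-up, the last value is carried to the remaining months.

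**The concern.** A responder percentage can be read only if the limit and its basis are clear. Three things blur them here.

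- The limit at Month 36 is three times the only limit in the protocol. Neither section 12 nor the SAP's table of changes (section 2.1) explains the scaling or says that the protocol has none.
- A rising limit is applied to values that may have stopped moving because they were carried forward.
- Each rule is explained by a phrase that, taken literally, describes an absolute score.

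At stake is whether a late responder rate reflects slow progression, a looser limit or an old value. The SAP expects about 10 patients per genotype (section 4), so one patient moves a rate by 10 percentage points.

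**Working it through.** **1. Reproduce the SAP schedule.** Take the protocol's 4 and 2 as 12-month limits and scale by month/12: NIS limit = 4 × m/12, NIS-LL limit = 2 × m/12. For a patient worsening at a constant rate, a fixed NIS limit of 4 at month m allows an annual rate below 4 × 12/m.

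| Month | SAP limits | 4m/12 and 2m/12 | Ratio to 4/2 | Annual NIS rate passing the SAP | Annual NIS rate passing a fixed <4 |
|---|---|---|---|---|---|
| 6 | 2/1 | 2/1 | 0.5 | <4 | <8.00 |
| 12 | 4/2 | 4/2 | 1.0 | <4 | <4.00 |
| 18 | 6/3 | 6/3 | 1.5 | <4 | <2.67 |
| 24 | 8/4 | 8/4 | 2.0 | <4 | <2.00 |
| 36 | 12/6 | 12/6 | 3.0 | <4 | <1.33 |

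The schedule matches at all five months.

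**2. If the protocol limits are fixed.** On NIS, steady worsening of 2.67 to <4 points a year at Month 18, 2.00 to <4 at Month 24 and 1.33 to <4 at Month 36 fails the fixed limit and passes the SAP's. For example, +3 a year is +9 at Month 36. At Month 6 the direction reverses: 4 to <8 a year passes the fixed limit and fails the SAP's.

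The documents give no mean or SD, so the size in patients can only be illustrated. Assume normal annual NIS change with mean 0, 2 or 4 and SD 3 or 6, NIS-LL with half the mean and 0.6 times the SD, correlation 0.8, and straight-line change over time. The composite rate at Month 36 is then 40–84% by the SAP and 13–56% by the fixed rule. At Month 12 the two are identical. At Month 6 they are 40–84% and 64–98.5%.

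**3. If the protocol limits are a 12-month criterion.** The scaling alone then changes nobody with steady progression. Now add carry-forward. Take one follow-up at month 14 with NIS +5, and take change at a carried month as the carried value minus the start value. The monthly change is 5/14 = 0.357.

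| Month | NIS change used | SAP limit | SAP result | Fixed <4 |
|---|---|---|---|---|
| 6 | 5 × 6/14 = 2.14 | 2 | fail | pass |
| 12 | 5 × 12/14 = 4.29 | 4 | fail | fail |
| 18 | 4.29 or 5, carried | 6 | pass | fail |
| 24 | same | 8 | pass | fail |
| 36 | same | 12 | pass | fail |

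The result is the same whether the interpolated or the observed value is carried. More generally, with an observed change d at month 14, the patient fails at Month 12 when 12d/14 ≥ 4, that is d ≥ 4.67. If d is the value carried, the patient passes the NIS limit at Month 36 whenever d < 12. The composite follows the same path if NIS-LL stays within its limits: NIS-LL +1 at month 14 gives 0.43 at Month 6, 0.86 at Month 12 and at most 1 thereafter.

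**4. NIS-only against composite at Month 12.** NIS +3 with NIS-LL +2 is a responder under SAP 12.1 and a non-responder under the 4/2 composite. Among patients with both scores, every composite responder is also a NIS-only responder, so the NIS-only rate is at least as high. Under the assumptions of step 2 the excess is 7–11 percentage points, about one patient in 10.

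**5. Change against absolute score.** NIS runs from 0 to 244 (SAP 9.1.1). A patient going from 20 to 22 has a change of +2 and is a responder by the change rule, but has a score of 22 and fails a literal limit of 4 points. Because the starting score cannot be negative, a score below 4 always implies a change below 4. The absolute reading can therefore only remove responders.

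**The case against.** The strongest reply is that the SAP fills a gap sensibly. The protocol names no month, 4/2 is kept unchanged at Month 12 for both genotypes, and the schedule holds one annual rate throughout. A fixed limit would be lenient at Month 6, where it admits nearly 8 NIS points a year. All of this stands, and it means that fixed 4/2 should not be presented as the protocol's only possible meaning.

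A reader might infer that the SAP replaces the protocol rule, or that protocol failures are reported as responders. The first is not so at Month 12. The second follows only if the protocol limits are fixed, which it does not say.

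A reader might also infer that NIS-LL was dropped from the primary endpoint, or that the amendment clause in protocol 9.7 was breached. The documents do not support either. The primary objective never had a responder rule, the NIS change analysis remains, and the NIS-only rate is an addition listed in the SAP's table of changes. SAP 3.2.1 also cites an archive note that is not among the documents.

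Nor is it true that a NIS-only rate can never be below the composite as tabulated. The composite is missing if either score is missing, and subgroup tables show valid percentages only. For example, NIS-only 6/10 = 60% against composite 6/8 = 75% if two NIS failures lack NIS-LL.

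On carry-forward, SAP section 6 says missing data are not imputed and section 12.2.1 leaves incomplete data missing. But 12.2.1 sends the reader to section 6.1 for the monthly values, and 6.1.1 carries the last value forward.

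Finally, the study is descriptive, and SAP 10.3.1 plans monthly NIS change and a per-patient NIS listing. A reader could apply a fixed NIS limit from that listing, but not the composite, because no such listing is planned for NIS-LL.

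**Conclusion.** The point holds as a defect of definition and labelling that is worth correcting. The scaling is exact (half at Month 6, three times at Month 36) and unexplained. On the fixed reading it moves steady progressors of 1.33 to <4 NIS points a year across the NIS limit at Month 36, and it is stricter at Month 6. On the 12-month reading the annual rate is unchanged, yet carry-forward against a rising limit still turns Month 12 failures into later responders without new data. How many patients this affects depends on how many have a single follow-up that ends before the later months; the documents do not say, though protocol 9.9 expects scarce follow-up data. The rates in steps 2 and 4 of the working rest on assumed distributions and only illustrate the size. The absolute-score wording contradicts the change rule on either reading.

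**What to change.** In SAP 12.1 and 12.2:

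1. State that every limit applies to change from the start of treatment, and reword each explanatory phrase to say that the patient's change is below the limit.
2. At every month, tabulate the fixed 4/2 composite beside the month-scaled composite. Give the reason for scaling, and label the scaled and NIS-only rules as added by the SAP.
3. Do not judge a carried-forward value by a later, larger limit. Set responder status to missing at that month, or use the limit for the month in which the value was observed.
4. Show the Month 12 NIS-only and composite rates together, on the patients who have both scores.
5. Correct the Month 36 entry under NIS-LL, which repeats the composite, or say that this is intended.

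The cost is SAP wording and a few table rows from data already held. Late-month responder rates may look less favourable, and setting carried values to missing reduces the number of patients at those months.

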9.2. Setting

The current study population consists of ATTRv and ATTRwt patients who have participated in studies B3461028 and B3461045 in Spain, with cardiac and neurologic involvement receiving or have received tafamidis free acid 61 mg for at least 12 months, and who are in neurological

PFIZER CONFIDENTIAL

follow-up for no less than 12 months. To our knowledge, 17 ATTRv patients have been included in these studies.

Individuals participating in the TRAMA study must meet all of the inclusion and none of the exclusion criteria described in Section 9.2.1.

9.2.1. Inclusion criteria

Patients must meet all of the following inclusion criteria to be eligible for inclusion in the study:

[figure not shown]
1. Be of legal age (>18 years).
2. Have participated in studies B3461028 and/or B3461045 in Spain.
3. Have been treated for at least 12 months with tafamidis free acid 61 mg.
4. Have a minimum of 12 months of neurological follow-up after starting treatment with tafamidis free acid 61 mg and have data from previous neurological evaluation or at the time of starting treatment with tafamidis free acid 61 mg.
5. Have been diagnosed with ATTR amyloidosis polyneuropathy (ATTR-PN), based on any of the following criteria:
 - a. Decreased amplitude in EMG studies, at least two nerves below normal, excluding median, or other nerve entrapment sites.
 - b. A reduction in amplitude by more than 50% by at least two nerves above the patient's baseline value, excluding the median.
 - c. Two different altered fine fiber tests (Sudoscan, CRS, RR interval variability, skin biopsy...).
 - d. A clinic compatible with small fiber neuropathy (painful or dysautonomic) and an altered fine fiber test.

9.2.2. Exclusion criteria

Patients meeting any of the following criteria will not be included in the study:

1. Treatment with tafamidis free acid 61 mg for less than 12 months.
2. Not having a minimum of 12 months of neurological follow-up after starting treatment with tafamidis free acid 61 mg.
3. Etiological diagnosis of polyneuropathy other than ATTR.

PFIZER CONFIDENTIAL

9.3. Variables

The variables to be collected from each patient at participating sites will be:

- Clinical parameters available in their medical history in the 12 months prior to their inclusion in studies B3461028 and/or LTE (B3461045).
- Clinical parameters available in their medical history at the time of inclusion in studies B3461028 and/or LTE (B3461045) (last visit to the site before inclusion in the study).
- Routine follow-up visits (up to the last available visit prior to enrollment in the TRAMA study).

The variables to be collected from each individual's medical history during the course of this study will be:

- **Treatment-related variables:**

- Date of consent signature for entry into study B3461028 and B3461045
- ATTR Treatment Start Date:
 - Initiation of treatment with commercial medication (tafamidis 20 mg)
 - Treatment regimen in the trial of ATTR-ACT or LTE tafamidis 20 mg
 - Treatment regimen in the ATTR-ACT or LTE tafamidis 80 mg or 61 mg trial
- Patient is currently on treatment with tafamidis free acid 61 mg (if not, specify stop date)

- **Demographic variables:**

[figure not shown]
- Age, gender
- Genotype: mutations (homozygosity/heterozygosity) or wt
- Age of disease onset (in order to characterize whether the disease onset was neurological or cardiological and to understand why it was not treated with available therapeutic options)
- First disease-related sign or symptom
- Age at disease diagnosis

- **Variables collected at each follow-up visit:**

- **Extra-cardiac 'red flags' medical history:**

- Carpal tunnel syndrome (if yes, if there was a surgery/date)
 - Lumbar stenosis
 - Gastrointestinal disturbances: diarrhea/constipation, early satiety

PFIZER CONFIDENTIAL

- Urological disturbances: urinary tract infections, urinary incontinence, urinary infections, incomplete emptying sensation
- Ophthalmological disturbances
- Central nervous system (CNS) disturbances (seizures, stroke or transient ischemic attack, cognitive impairment)
- Symptoms of autonomic neuropathy: impaired sweating, sexual dysfunction, orthostatic hypotension
- Symptoms of peripheral neuropathy (allodynia, paresthesia, hyperalgesia...)
- Unintentional weight loss

- Modified Body Mass Index (mBMI)
- Neurological variables:
 - NIS (*Neuropathy Impairment Score*)
 - NIS-LL (*Neuropathy Impairment Score Lower Limbs*)
 - PND (*Polyneuropathy disability score*)
 - FAP (*Family Amyloidotic polyneuropathy stage*)
- Neurophysiological variables:
 - NCS (EMG): sural sensory nerves, ulnar, tibial and peroneal motor
 - CCE - Sudoscan (feet and hands, if available)
 - R-R Range Variability
- Scales:
 - Norfolk QoL-DN (*Norfolk Quality of Life-Diabetic Neuropathy*)
 - FAP-RODS (*Familial Amyloid Polyneuropathy Specific Rasch-Built Overall Disability Scale*)
 - COMPASS-31 (*Composite Autonomic Symptom Score 31*)
- Renal Assessment Variables:
 - Proteinuria, albuminuria/microalbuminuria; eGFR
 - Creatinine Clearance
- Ophthalmologic Assessment Variables:
 - Intraocular pressure
 - Glass opacity classification

Variable	Role	Source Document(s)	Operational Definition
Date of birth	Baseline Characteristic	Medical Record	The investigator will collect the data in the CRF reflecting the information included in the medical record
Sex			
Genotype: mutation (homozygous/heterozygous) or wt			
Age at onset of the disease	Subgroup Identifier	Medical Record	The investigator will collect the data in the CRF reflecting the information included in the medical record
First sign or symptom of disease			
Age at disease diagnosis			
Date of consent signature for entry into study B3461028 and B3461045	Subgroup Identifier	Medical Record	The investigator will collect the data in the CRF reflecting the information included in the medical record
ATTR Treatment Start Date			
Treatment regimen in the trial of ATTR-ACT origin (tafamidis 80 mg or 61 mg)			
Carpal tunnel syndrome (if yes, if there was a surgery/date)	Result	Medical Record	The investigator will collect the data in the CRF reflecting the information included in the medical record
Lumbar stenosis			
Gastrointestinal disturbances: diarrhea/constipation, early satiety			
Urological disturbances			
Ophthalmological disturbances			
Central Nervous System (CNS) Disorders			
Symptoms of autonomic neuropathy: impaired sweating, sexual dysfunction, orthostatic hypotension			
Symptoms of peripheral neuropathy (allodynia, paresthesia, hyperalgesia...)			
Unintentional weight loss			
mBMI	Result	Medical Record	The investigator will collect the data in the CRF reflecting the information included in the medical record or calculated from the medical record data
mBMI (modified BMI) corrects hypoalbuminemia effects, thus better reflecting nutritional health (mBMI=BMI x albumin level)			

PFIZER CONFIDENTIAL

NIS	Result	Medical Record	
NIS (Neuropathy Impairment Score) is a clinically important, sensitive measure of individual neurological function, assessing sensory function, reflexes, and muscle weakness			
NIS-LL			
NIS-LL (Neuropathy Impairment Score Lower Limbs) is a clinically important, sensitive measure of neurological function in individuals, assessing sensory function, reflexes, and muscle weakness of the lower limbs			
PND	Result	Medical Record	The investigator will collect the data in the CRF reflecting the information included in the medical record or calculated from the medical record data
PND (Polyneuropathy disability score) is a simple staging system according to the degree of neuropathic dysfunction and its impact on ambulation			
FAP	Result	Medical Record	
FAP (Family Amyloidotic polyneuropathy stage) is a staging system based on symptom severity and disease progression			
NCS (EMG): sural sensory, ulnar, tibial and peroneal nerves	Result	Medical Record	
CCE - Sudoscan (feet and hands)			The investigator will collect the data in the CRF reflecting the information included in the medical record
Electrochemical Cutaneous Conductance allows us to measure autonomic sudomotor function in a non-invasive, rapid and accurate manner			
CVR-R			
The coefficient of variation of the R-R interval is a measure of cardiovascular autonomic dysfunction. It is calculated as the standard deviation percentage of the R-R intervals divided by their mean			

Norfolk QoL-DN	Result	Medical Record	
Norfolk Quality of Life Questionnaire for Diabetic Neuropathy is a standardized and validated instrument that assesses the effect of polyneuropathy on the functionality and quality of life of the individual			
FAP-RODS			The investigator will collect the data in the CRF reflecting the information included in the medical record
FAP-RODS (Familial Amyloid Polyneuropathy Specific Rasch-Built Overall Disability Scale) is a questionnaire that assesses the effect of neuropathy on daily activities	Result	Medical Record	
COMPASS-31			
COMPASS-31 (Composite Autonomic Symptom Score 31) is a questionnaire designed to assess the severity and functional ability in patients with autonomic dysfunction			
Proteinuria			
Albuminuria/microalbuminuria levels	Result	Medical Record	The investigator will collect the data in the CRF reflecting the information included in the medical record
eGFR (estimated Glomerular Filtration Rate)			
Creatinine Clearance	Result	Medical Record	The investigator will collect the data in the CRF reflecting the information included in the medical record
Intraocular pressure			
Glass opacity classification			

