8.1.1 ATTR Treatment Start Date

Frequencies (N. %) will be shown for the following qualitative variables:

- Commercial medication (Tafamidis 20 mg) (Yes / No)
- Treatment regimen in ATTR-ACT (B3461028) or LTE (B341045) trial of origin (multiple choice table):
 - ATTR-ACT or LTE Tafamidis 20 mg
 - ATTR-ACT or LTE Tafamidis 80 mg
 - ATTR-ACT or LTE Tafamidis 61 mg
- Is the patient currently on Tafamidis free acid 61 mg? (Yes / No)

Descriptive statistics (Mean, SD, Median, Minimum, Maximum, Q1, Q3 and N) of the following quantitative variables will be displayed:

- Duration for the following treatments (in months):
 - ATTR-ACT or LTE Tafamidis 20 mg, calculated as end date - start date.
 - ATTR-ACT or LTE Tafamidis 80 mg, calculated as end date - start date.
 - ATTR-ACT or LTE Tafamidis 61 mg, calculated as end date - start date. If still on treatment, up to the enrollment date will be considered (enrollment date - start date).

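### The listed treatment variables cover only tafamidis products, and the 61 mg stop date that is collected is not applied to the efficacy values

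*Protocol*

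**What the plan says.** **Treatments recorded.** Under treatment-related variables, Protocol 9.3 asks for the parent-study consent dates and then four treatment items:

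- the start of the marketed product, worded as "Initiation of treatment with commercial medication (tafamidis 20 mg")
- which lower-dose (20 mg) regimen, if any, the patient had in the parent studies
- which higher-dose regimen (80 or 61 mg) the patient had there
- present use and its end, worded as "Patient is currently on treatment with tafamidis free acid 61 mg (if not, specify stop date")

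SAP 8.1.1 reports "Commercial medication (Tafamidis 20 mg) (Yes / No"), the trial regimens and "Is the patient currently on Tafamidis free acid 61 mg? (Yes / No"). It gives durations for trial 20, 80 and 61 mg, but none for commercial 20 mg. Neither document lists another ATTR-directed treatment or a symptomatic drug as a variable, exclusion, censoring event or covariate. Protocol 9.9 does not name this as a limitation. The nearest exclusion, "Etiological diagnosis of polyneuropathy other than ATTR", concerns the cause of the neuropathy, and SAP 5 does not check it against the CRF.

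**Who is followed, and how long.** Protocol 9.2 and 9.5 admit current and past users of 61 mg with at least 12 months of treatment. Protocol 9.3 takes follow-up to the last visit before TRAMA enrolment, not to the end of 61 mg.

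**How values are formed.** SAP 6.1.1 draws a straight line from the start value to the first follow-up and reads off Months 6 to 36 as far as that visit reaches. If only one follow-up exists, its value is carried to the end. Treatment status plays no part. SAP 5 and 8.1.1 use the 61 mg end date, but only for eligibility and duration.

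**The concern.** The stated objectives are to determine the efficacy of 61 mg, in one group with no control. A change in NIS can be credited to 61 mg only if nothing else acting on the neuropathy changed over the same interval. The plan neither records the main alternative explanation, another ATTR-directed treatment, nor separates values measured after 61 mg ended from those measured during it.

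The two gaps differ. For an added treatment the information is missing from the listed variables, so no analysis can recover it. For a switch, the end of 61 mg is known and only its successor is not. There the problem is an analysis rule that ignores a date the study holds. What is at stake is whether the Month 12 to 36 tables describe 61 mg or a mixture of 61 mg and unrecorded later treatment.

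**Working it through.** The plan states no power or sample-size calculation, so there is no figure to reproduce. The check is how far a treatment change can travel through SAP 6.1.1.

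**Inputs from the documents.** 10 expected ATTRv patients (SAP 4); at least 12 months on 61 or 80 mg (SAP 5); the interpolation and carry-forward rules (SAP 6.1.1); NIS responder limits, read as change from start, of <2, <4, <6, <8 and <12 points at Months 6, 12, 18, 24 and 36 (SAP 12.1, 12.2.1).

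**Assumed for illustration.** A patient worsens by 0.5 NIS points per month from the start of 61 mg, stops at Month 14, then changes by *s* points per month. The only NIS follow-up is at Month 24. The patient meets the 12-month treatment and follow-up requirements.

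**Step 1. Month 12.** The true change is 0.5 × 12 = 6.0, a non-responder. The change at Month 24 is 0.5 × 14 + 10*s* = 7 + 10*s*, so the SAP assigns (7 + 10*s*) / 24 × 12 = 3.5 + 5*s* at Month 12.

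| *s* after stopping | Change at Month 24 | SAP Month 12 change | Class (<4) |
|---|---|---|---|
| 1.0 | 17.0 | 8.5 | non-responder |
| 0.5 | 12.0 | 6.0 | non-responder |
| 0.25 | 9.5 | 4.75 | non-responder |
| 0 | 7.0 | 3.5 | responder |
| -0.25 | 4.5 | 2.25 | responder |

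The class flips when 3.5 + 5*s* < 4, that is, when *s* < 0.1.

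**Step 2. The other months, with *s* = 0.** The assigned changes are 7.0/24 × 6 = 1.75 (Month 6), 3.5 (Month 12), 7.0/24 × 18 = 5.25 (Month 18), 7.0 (Month 24) and 7.0 carried forward (Month 36). All five fall under their limits. The true changes at Months 6, 12 and 18 are 3.0, 6.0 and 7.0, all over their limits. One measurement taken 10 months after 61 mg ended sets the whole profile.

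**Step 3. The opposite direction.** Assume 0.3 points per month on 61 mg and 0.6 afterwards. The true Month 12 change is 0.3 × 12 = 3.6, a responder. The SAP gives (0.3 × 14 + 0.6 × 10) / 24 × 12 = 10.2/24 × 12 = 5.1, a non-responder.

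**Step 4. Weight in the group.** One patient is 1/10 = 10 percentage points, two are 20 and three are 30. For example, 7/10 has an exact 95% interval of 34.8 to 93.3%, and 6/10 has 26.2 to 87.8%. In the mean, altering one patient's change by 2, 4 or 8 points (assumed) moves the group by 0.2, 0.4 or 0.8. For three patients the shift is 0.6, 1.2 or 2.4.

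**Step 5. What simple exclusion would do.** If the Step 1 patient with *s* = 0 makes the count 7/10 where the truth is 6/10, dropping that patient gives 6/9 = 66.7%. This is still above 60%, because a progressor has been removed.

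**The case against.** Several points on the other side stand.

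- **A reader might infer that switched patients cannot be identified.** The documents do not support that. The 61 mg stop date and the visit dates are both held, so values after 61 mg can be separated at analysis. Only the replacement treatment is unrecorded.
- **A reader might infer that Month 12 is directly exposed to switching.** With 12 months of treatment required, an ordinary switch comes later. It touches Month 12 only through interpolation from a late first follow-up, as in Step 1.
- **A reader might infer that the bias favours 61 mg**, because progressors are the likeliest to receive something else. That is plausible but not shown; Step 3 goes the other way.
- **The remark "to understand why it was not treated with available therapeutic options"** might be read as an admission of competing treatment during follow-up. It explains why age at onset is collected and names no product.
- **The Yes/No item for commercial 20 mg** describes a table. Its start is collected under the treatment start date heading, so a start after 61 mg can be placed in time. What is not listed is a stop date.
- **Symptomatic drugs** bear mainly on Norfolk QoL-DN and COMPASS-31, which are secondary. NIS scores sensation, reflexes and weakness.

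It is also fair to say that the full CRF is not supplied, that the documents do not say whether the parent studies allowed other ATTR-directed treatment, and that the number of affected patients may be zero. The plan is largely descriptive, but a descriptive table presented as an efficacy result for 61 mg still depends on what the patients were taking.

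**Conclusion.** The point holds in this form: an ATTR-directed treatment added to 61 mg is invisible in the listed variables, the successor to 61 mg after a switch is not recorded, and the efficacy sections ignore the stop date that is collected. Values after a treatment change are therefore reported as 61 mg results.

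Switches matter mainly at Months 18 to 36, and at Month 12 when the first follow-up is late. Additions can matter at any month. Each reclassified patient is 10 percentage points of the responder rate if the expected 10 ATTRv patients are enrolled. How many patients are affected, and in which direction, cannot be derived from the documents. The slopes and stop time in the working are assumptions that show the mechanism, not estimates of its size. This is an inexpensive improvement that bears on what the study can conclude; the documents do not show that the results will be wrong.

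**What to change.** **CRF.** Add any other ATTR-directed treatment (yes/no, name, start date, stop date) and a stop date for commercial tafamidis 20 mg, both from the medical record already being abstracted. If CRF v1.0 already holds these fields, only the SAP needs to change.

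**SAP 6.1.1, 10.3, 10.5 and 12.** Keep the planned summary. Add a sensitivity summary restricted to values dated while on 61 mg and before any other ATTR-directed treatment. In it, do not interpolate or carry values across the 61 mg stop date or the start of another treatment. Flag affected patients in the per-patient NIS listing in SAP 10.3.1 and report how many there are, including if there are none.

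**Optional.** Flag changes in symptomatic medication when presenting Norfolk QoL-DN and COMPASS-31. This is secondary, and may be hard to date where Protocol 9.9 already expects scarce follow-up data.

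**Cost.** Slightly longer abstraction for about 20 charts (10 ATTRv and 10 ATTRwt), some SAP wording, and fewer values in the restricted summary. As Step 5 shows, that summary can under-represent progressors, so it should stand beside the main summary and not replace it.
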